9.3.2 Covariates

The relationship between covariates and efficacy endpoints may be explored if appropriate.

9.3.3 Subgroups

Subgroups will be prespecified in the statistical analysis plan.

9.3.4 Handling of Missing and Incomplete Data

Descriptive statistics will be used to identify the extent of missing data. Missing or incomplete dates that are critical to efficacy and safety analysis (eg, date of death, adverse event start date) will be imputed. Detailed imputation rules will be documented in statistical analysis plan.

9.4 Statistical Analyses

The statistical analysis plan will be developed and finalized before database lock. Below is a summary of the timing and methods for the planned statistical analyses. To preserve study integrity, the final analysis will be conducted and reported following the end of study, as defined in Section 4.4.1.

9.4.1 Planned Analyses

9.4.1.1 Interim Analysis and Early Stopping Guidelines

Safety data will be reviewed on an ongoing basis. During dose exploration and formally during DLRMs, Amgen, in consultation with the site investigators, will review all available cumulative data by dose level prior to making dose escalation or dose de-escalation recommendations. Adverse events and DLTs observed in all subjects will be evaluated continually and fully integrated into all DLRMs and considered in all enrollment and dosing decisions.

During dose expansion, Amgen will conduct evaluations of the grade 4 or higher treatment-related adverse event rate to assess if the threshold for possible early trial termination has been reached. If this threshold is met, enrollment to dose expansion will be halted pending review of safety data by the DLRT. After receiving the DLRT recommendation, Amgen will choose to take one of the following actions.

- 1) Terminate the trial
- 2) Resume Dose Exploration with a schedule as outlined in the protocol and recommended by the DLRT.
- 3) Amend the protocol to potentially improve the benefit/risk for subjects (eg, increase safety monitoring, modify dose/schedule, mandate premedication).
- 4) Continue dose expansion without any changes.

The stopping rules use a Bayesian approach proposed by Thall and colleagues (Thall et al, 1995) to terminate the study if the posterior probability that the grade 4 or higher treatment-related adverse event rate of greater than 20% is $> 80\%$. The stopping boundaries assume a prior distribution of Beta (0.40, 1.60) are presented in [Table 9-1](#) and the operating characteristics with pre-specified batch size of 10 new subjects per batch are presented in [Table 9-2](#). The operating characteristics in [Table 9-2](#) provide the probability of stopping the trial early for given hypothetical true rate of grade 4 or higher treatment-related adverse events, whereas the stopping criteria in [Table 9-1](#) are based

on situations where the empirical evidence would result in a posterior probability of $\geq 80\%$ that the true grade 4 or higher treatment-related adverse event rate is $\geq 20\%$.

Table 9-1. Stopping Boundary for Dose Expansion with Posterior Probability of 80% and Grade 4 or Higher Treatment-related Adverse Event Limit of 20%

Number of Subjects	Stop Subjects if Observing This Many Grade 4 or Higher Treatment-related Adverse Events
10	≥ 4
20	≥ 6
30	≥ 9
40	Dose Expansion Complete

Table 9-2 Operating Characteristics with Batch Size of 10 Subjects

True Grade 4 or Higher Treatment-related Adverse Event Rate	Probability of Early Stopping of Dose Expansion	Average Dose Expansion Sample Size
0.10	2.0%	39.5
0.15	9.7%	37.6
0.20	25.8%	33.9
0.25	47.7%	28.8
0.30	69.2%	23.4

Interim futility analyses (non-binding) will be performed in a continuous manner using Bayesian predictive probability (Lee & Liu, 2008). Interim futility analyses in Part 2 will begin after approximately 20 subjects have been treated and has a minimum potential follow-up of 9 weeks. Interim futility analyses will be based on the ORR analysis set. Following this initial interim futility analysis, subsequent interim futility analyses will be performed after every 10 subjects in Part 2 have reached the data cutoff criteria, until all subjects are enrolled and evaluated. For interim futility analyses a response is defined as either a confirmed or unconfirmed CR or PR per RECIST 1.1. For the final analysis, a response is defined as a confirmed CR or PR per RECIST 1.1.

The Target Value (TV) is set to demonstrate a 18% increase in ORR (ie, TV = 30%) over the benchmark 12% ORR. For Part 2, at final analysis:

- NoGo criteria will be met if the probability that the true ORR exceeds the pre-specified TV of 30% is less than 5% (ie, NoGo: $P[\text{ORR} > \text{TV}] < 5\%$).

Given the existing observed data during the continuous monitoring stage, the Bayesian predictive probability is obtained by calculating the probability of reaching a NoGo decision should the treatment group be enrolled and evaluated to the maximum planned final sample size of 40 in Part 2. Further enrollment may be terminated if futility criteria are met. Notice the NoGo criteria is for interim futility analysis purpose only.

- Futility is met if it is predicted that there is a high probability of reaching a NoGo decision upon full enrollment of 40 subjects in Part 2 given the existing observed data (ie, predictive probability of a NoGo decision $> 95\%$).

The decision matrix for continuous monitoring of ORR is provided in [Figure 9-1](#) assuming a prior distribution of Beta (1, 1). For example, given TV of 30%, 3 or fewer observed responders after 30 subjects have reached the data cutoff criteria would trigger stopping enrollment claiming futility due to a high probability of reaching a NoGo decision upon full enrollment to 40 subjects given the existing observed data.

Figure 9-1. Decision Matrix for Continuous Monitoring of ORR

Operating characteristics of this continuous monitoring method are presented in [Table 9-3](#) and are based on 100 000 simulations using the prespecified TV value, and NoGo and Futility definitions.

A false NoGo is defined as observing either futility criteria during the continuous monitoring stage or NoGo criteria at final analysis when the true ORR is greater than or equal to the TV (ie, False NoGo: $P[\text{Futility or NoGo Decision} \mid \text{True ORR} \geq \text{TV}]$).

Table 9-3. Guidelines for Futility Analysis

True ORR (BM ORR = 12%)	Probability of Futility	Expected N	% Decision Prior to Final
10%	96%	29	67%
15%	76%	35	35%
20%	44%	38	14%
25%	19%	39	5%
30%	6%	40	1%
35%	1%	40	0%
40%	0%	40	0%

BM ORR = benchmark objective response rate; TV = target value.
 Criteria: Target Value (TV) =30%; NoGo: $\text{Pr}(\text{ORR} > \text{TV}) < 5\%$; Futility: $\text{PP}(\text{NoGo}) > 95\%$
 Frequency: 10 subjects; BM ORR: Benchmark Objective Response Rate

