Appendix D. BOR per RECIST 1.1

BOR by investigator will be derived based on the timepoint response collected in the RECIST 1.1 CRF. BOR by central review will be derived from timepoint response shared by the central imaging vendor. At each time point, BOR will be derived based upon the evaluated timepoints up to and including the current MRI/CT assessment. The following rules will apply to BOR:

- CR is better than PR is better than SD is better than PD is better than NE
- For a BOR of SD, a duration of ≥ 49 days since the cycle 1 day 1 is required
- For a BOR of CR or PR confirmation is required. PR can be confirmed by a PR or CR. The confirmation assessment must be in a consecutive assessment ≥ 28 days after the initially observed assessment of CR or PR except the following cases:
 - An unlimited number of intermittent assessments of NE or CR <28 days can
 occur between the initial response and the confirmation of CR. For example,
 BL, CR, NE, NE, NE, CR the CR at post-baseline 1 is confirmed at postbaseline 5. SD is not allowed between CR and subsequent confirmation CR.
 - An unlimited number of intermittent assessments of NE, SD, PR or CR <28
 days can occur between the initial response and the confirmation of PR. For
 example, BL, PR, SD, SD, SD, PR the PR at post-baseline 1 is confirmed at
 post-baseline 5.

Table 14-3 provides the BOR determination per RECIST 1.1 where confirmation of response (CR/PR) is required. Table 14-4 outlines the steps to derive Confirmed_BOR (step 1) given timepoint assessments.

At interim futility analyses, due to lack of sufficient follow-up time for confirmation scan, study team may choose to report both confirmed responders and unconfirmed responders (subjects had an initial PR or CR and still has potential for future confirmative scans). Interim_BOR is defined to include unconfirmed responders in addition to those who achieve Confirmed_BOR. Table 14-4 step 2 provides details to derive the unconfirmed responders.

Table 14-3. BOR per RECIST 1.1 where Confirmation of CR/PR is Required

Criterio n	T1 .	days after	Timepoint T2 Response	T2 ≥ 49 days after	T2 ≥ 28 days after T1?	BOR_temp
	Response		response	C1D1?	uitoi i i i	

Date: 24 March 2023 Page 50 of 53

	1					
C1	CR	Yes	CR	-	Yes	CR
C2			CR	-	No	SD
C3			PR, SD	-	-	Query data*
C4			PD	-	-	SD
C5			NE, No furth	ner evaluat	ions	SD
C6		No	CR	-	Yes	CR
C7			CR	Yes	No	SD
C8			CR	No	No	NE
C9			PR, SD	-	-	Query data*
C10			PD	-	-	PD

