tumor assessment (i.e. had PD,	(i.e. no PD, next therapy, or end of study),	
next therapy, or end of study):	unconfirmed PR/CR can be considered	
	responders.	
Assign Interim_BOR =	If any scan is CR and haven't got the	
Confirmed_BOR	opportunity to receive next scan, then	
	Interim_BOR = CR.	
	If any scan is PR and haven't got the	
	opportunity to receive next scan, then	
	Interim_BOR = PR.	
	Else, Interim_BOR = Confirmed_BOR at the	
	latest scan.	

Date: 24 March 2023 Page 52 of 53

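### The interim futility response is defined more loosely in Protocol 9.4.1.1 and SAP 7.1 than in SAP Appendix D, and the early-stop and expected-N columns of Tables 9-3 and 7-3 assume interim and final responses are the same variable

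*Protocol*

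**What the plan says.** Protocol 9.4.1.1 sets the interim numerator: "For interim futility analyses a response is defined as either a confirmed or unconfirmed CR or PR per RECIST 1.1". The next sentence sets the final one: "For the final analysis, a response is defined as a confirmed CR or PR per RECIST 1.1". SAP 7.1 makes the same pair of statements, applied to each Part 2 group of 40. Neither section limits which unconfirmed responses count, and neither refers to Appendix D at that point.

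SAP Appendix D is narrower. It describes the unconfirmed responders as those who "subjects had an initial PR or CR and still has potential for future confirmative scans", and leaves it to the study team whether to report them alongside confirmed responders. Table 14-4 step 2 turns this into a derived variable, Interim_BOR:
- Subjects who have stopped tumour assessment (PD, next therapy or end of study) take their confirmed best response.
- For the rest, a CR or PR counts only if the next scan has not yet been possible.
- All other cases fall to the clause beginning "Else, Interim_BOR = Confirmed_BOR at the".

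The futility rule predicts the NoGo decision at 40 subjects: a Beta(1,1) prior, NoGo if P(ORR > 30%) < 5%, and futility if the predictive probability of NoGo exceeds 95%. The operating characteristics are described as "based on 100 000 simulations using the prespecified TV value, and NoGo and Futility definitions". No confirmation rate and no second response definition is mentioned.

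**The concern.** A predictive probability carries today's responders forward as final responders. If some responses counted at a look can never become confirmed, the forecast is of a different quantity from the NoGo it is meant to predict, and an inactive regimen is less likely to stop early. The boundaries are low, 1 of 20 and 3 of 30. When the count sits on the boundary, one non-confirming response is enough to continue enrolment, by 10 subjects to the next look or by up to 20 to the cap.

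Two things are at stake. First, the numerator of a stopping rule can be read two ways, and the looser reading can include a PR already followed by PD. Such cases can exist at a look: nine weeks is only the minimum potential follow-up and scans are every 8 weeks, so the earliest subjects may have had a second scan. Second, readers of Table 9-3 will take its % Decision Prior to Final and Expected N columns as what the rule delivers.

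**Working it through.** **Inputs.** From Protocol 9.4.1.1: the prior, thresholds and maximum of 40 given above, with looks at 20 and 30. From Protocol Table 1-3: scans every 8 ± 1 weeks and confirmation at least 4 weeks after first response. Assumed, because the documents do not give them: the confirmation rate *c*, the number of subjects pending at a look, and the share *l* of responses first seen after a look.

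**Step 1: boundaries.** With *x* responders of 40 the posterior is Beta(1+x, 41−x).
- P(ORR > 0.30) is 0.0458 at x = 7 and 0.0943 at x = 8, so NoGo is 7 or fewer.
- The beta-binomial predictive probability of NoGo at n = 20 is 0.982 with 1 responder and 0.897 with 2.
- At n = 30 it is 0.987 with 3 and 0.918 with 4.

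Futility is therefore 1 or fewer of 20 and 3 or fewer of 30. The second agrees with the protocol's own example.

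**Step 2: reproduce Table 9-3 with one response variable.** At a true ORR of 10%:
- Stop at 20: 0.9^20 + 20 × 0.1 × 0.9^19 = 0.392.
- First stop at 30: 0.276.
- Early stop: 0.392 + 0.276 = 0.668 (stated 67%).
- Expected N: 40 − 20 × 0.392 − 10 × 0.276 = 29.4 (stated 29).
- Overall futility: 95.9% (stated 96%).

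The other rows also agree, for example 34.8% / 76.0% / 34.8 at 15% and 1.4% / 5.9% / 39.8 at 30%. The table thus treats a response counted at a look and a final response as the same thing.

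**Step 3: literal text.** Every initial response counts at a look, so the counted rate is r = p/c. With p = 10% and c = 80%, r = 0.125. P(Bin(20, 0.125) ≤ 1) = 0.267 and first stop at 30 is 0.232. Early stop is 0.267 + 0.232 = 0.499, and expected N is 40 − 5.34 − 2.32 = 32.3.

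**Step 4: Appendix D.** Assume the latest 10 subjects are pending. The count at look n is Bin(n−10, p) + Bin(10, p/c). With c = 80%, stop at 20 is 0.325, first stop at 30 is 0.292, and early stop is about 0.616.

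Results at a true confirmed ORR of 10% (stated: 67%, N = 29):

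| Assumed confirmation rate | Literal: early stop / expected N | Appendix D: early stop / expected N |
|---|---|---|
| 90% | 59.2% / 30.8 | 64.5% / 29.9 |
| 80% | 49.9% / 32.3 | 61.6% / 30.6 |
| 70% | 38.8% / 34.1 | 57.9% / 31.4 |
| 60% | 26.5% / 36.0 | 52.8% / 32.4 |

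At a true 15% (stated 35%) the literal text gives about 26/18/11/5% and Appendix D about 32/29/25/20%. In all these cases overall futility stays at about 96% for a true 10% and about 6% for a true 30%, because the final decision uses confirmed responses either way.

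**Step 5: late responses.** Let a share *l* of confirmed responses in the latest 10 subjects be invisible at the look. Their counted rate becomes p(1−l) + (p/c − p). With c = 80% and l = 20% this is 0.08 + 0.025 = 0.105. Stop at 20 is 0.378, first stop at 30 is 0.292, and early stop is 0.669, about 67% and level with the table. With c = 90% and l = 20% it is about 70%, above the table.

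**The case against.** The strongest reply is that Appendix D already answers the question. Sections 9.4.1.1 and 7.1 are the short statement and Table 14-4 step 2 is the derivation, and that derivation drops failed confirmations. A reader might infer from the protocol sentence that the planned analysis will count responses known to have failed. The documents do not support that, because Interim_BOR reverts to the confirmed result in those cases. This part of the reply stands, and the 59/50/39/27% series belongs only to the literal text.

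A reader might also infer that the early-stop rates in Table 9-3 will not be achieved. That is not shown either. It depends on a confirmation rate the documents do not give, and late responses offset or reverse the loss, as step 5 shows.

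Counting pending responses is itself sound: a week-8 response cannot be confirmed by week 9. A confirmed-only numerator would raise early stopping at a true ORR of 30% from 1.4% to 3.2/5.4/19.3% with 3/5/10 subjects not yet confirmable. The looks are non-binding and no hypothesis is tested.

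The reply does not remove the ambiguity. SAP 7.1, the SAP's own decision-rule section, keeps the unrestricted wording. Appendix D makes reporting such responders optional. The SAP was written for protocol amendment 6, and amendment 7 still carries the unrestricted sentence. Appendix D's text and its table also differ slightly: a PR followed by SD can still be confirmed later, so the text's potential for future scans is wider than the table's next-scan test.

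**Conclusion.** The point holds as a matter of definition and labelling. The interim response has a loose statement in Protocol 9.4.1.1 and SAP 7.1 and a stricter, optional one in Appendix D, and the early-stop and expected-N columns rest on an idealisation that is not stated.

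At a true confirmed ORR of 10%, following the literal text costs about 8 to 40 points of early stopping (67% down to 59–27%) for confirmation rates of 90% to 60%. Under Appendix D with 10 subjects pending and no late responses the loss is about 2 to 14 points (67% down to 65–53%), and with late responses it can vanish or change sign. These figures rest on assumed confirmation rates, pending numbers and late-response shares. The probability-of-futility column, including the 6% at a true 30%, is essentially unaffected.

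**What to change.** 1. In Protocol 9.4.1.1 and SAP 7.1, define the interim futility response as a confirmed CR/PR, or an unconfirmed CR/PR whose confirmatory scan is still pending, and name Interim_BOR (SAP Table 14-4 step 2) as the variable.
2. In SAP Appendix D, replace the team's option with this rule for the futility count, so that the text and the table give the same answer.
3. Re-simulate the early-stop and expected-N columns of Tables 9-3 and 7-3 over a stated range of confirmation and late-response rates. Alternatively, label them as assuming that all interim responses confirm and none appear later.

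The cost is wording and one simulation. The boundaries, sample size and final analysis do not change. The stated early-stop rates may become slightly less favourable.

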9.4.1.1.1 Criteria for Evaluating Treatment With Siltuximab

Amgen will conduct evaluations of the treatment and outcome of the CRS events treated with siltuximab on an ongoing basis to assess if the threshold for evaluating siltuximab treatment has been reached as outlined in the [Table 9-4](#). If these criteria are met, an ad hoc DLRM will be triggered to review safety data and available pharmacokinetic, pharmacodynamics, and efficacy data. If recommended by DLRT, the use of siltuximab will resume. The criteria to trigger an adhoc DLRM to review siltuximab treatment use a

Bayesian approach proposed by Thall et al, 1995; an adhoc DLRM will be triggered if the posterior probability that the CRS progression to Grade 3 rate of greater than 20% is > 80% or the posterior probability that the CRS progression to Grade 4 rate of greater than 7.5% is >80%; or observation of any grade 5 CRS after the event has been treated with siltuximab. The boundaries presented below assume a prior distribution of Beta (0.4, 1.6) for progression to grade 3 CRS and a prior distribution of Beta (0.15, 1.85) for progression to grade 4 CRS. The evaluations could occur more frequently if necessary to address emerging safety concerns. If the triggered ad hoc DLRM coincide with regular DLRM, they may be combined.

Table 9-4. The Criteria for Evaluating the Use of Siltuximab

Number of subjects treated with siltuximab	Trigger DLRM if severity of any CRS event treated with siltuximab progresses to Grade 5	
	Or this number of subjects with severity of CRS progressed to Grade 3 after being treated with siltuximab	Or this number of subjects with severity of CRS progressed to Grade 4 after being treated with siltuximab
5	≥ 3	≥ 2
10	≥ 4	≥ 2
15	≥ 5	≥ 3
20	≥ 6	≥ 3
25	≥ 7	≥ 4
30	≥ 9	≥ 4
35	≥ 10	≥ 5
40	≥ 11	≥ 5

DLRM = Dose Level Review Meeting; CRS = cytokine release syndrome

9.4.1.2 Primary Analysis

The primary analysis for this subprotocol will occur when target enrollment is complete and each subject either completes at least 6 months on study or withdraws from the study.

9.4.1.3 Final Analysis

The final analysis will be performed after the last subject has had an opportunity to complete the corresponding end of treatment (EOT) visit/procedures.

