All subjects will be hospitalized for intensive monitoring for 48 hours post tarlatamab infusion during all cycle 1 doses. Hospitalization is not required for cycle 2 unless a subject experiences grade 2 or higher CRS or neurological events in cycle 1 (minimum of 24 hours hospitalization required post tarlatamab infusion on cycle 2 day 1 if grade 2 or higher CRS or neurological events are noted in cycle 1). The subjects may be discharged after this period if there are no signs and symptoms of CRS or other acute

toxicities. If subjects are not hospitalized during cycle 2, subjects will be observed for 8 hours post tarlatamab infusion.

Routine radiological imaging (computed tomography [CT]/magnetic resonance imaging [MRI]) and tumor burden assessments will be performed as outlined in the Schedule of activities. Assessment of disease response will be determined based on RECIST 1.1 per PCWG3 guidelines (Sections 11.8 and 11.9). To further assess the risk of delayed adverse events, the subject must return for safety follow-up (SFU) visit approximately 60 (+5) days after the last dose of tarlatamab.

Long-term follow-up will be conducted every 3 months up to 3 years from the first dose of tarlatamab for all subjects who have not withdrawn consent by clinic visit, telephone or chart review to assess for survival and/or the commencement of subsequent cancer therapy.

For a full list of study procedures, including the timing of each procedure, please refer to Section 8.2 and the Schedule of Activities in Section 1.3.

Statistical Considerations

All subjects who are enrolled and receive at least 1 dose of tarlatamab will be included in the analysis, unless otherwise specified.

The primary analysis will occur when target enrollment is complete and each subject either completes at least 6 months on study or withdraws from the study. The final analysis will be performed after the last subject has had an opportunity to complete the corresponding end of treatment visit/procedures.

Descriptive statistics will be provided for selected demographics, safety, pharmacokinetic, efficacy data by dose, dose schedule, and time as appropriate.

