4.4 End of Study

4.4.1 End of Study Definition

Primary Completion: The primary completion date is defined as the date when the last subject is assessed or receives an intervention for the final collection of data for the primary endpoint(s).

If the study concludes prior to the primary completion date originally planned in the protocol (ie, early termination of the study), then the primary completion will be the date when the last subject is assessed or receives an intervention for evaluation in the study (ie, last subject last visit).

End of Study: The end of study date is defined as the date when the last subject across all sites is assessed or receives an intervention for evaluation in the study (ie, last subject last visit), following any additional parts in the study (eg, long-term follow-up, [REDACTED]), as applicable.

Amgen will not continue provision of investigational product for subjects after their study participation ends unless it is a legal requirement.

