When a large, multicenter group has conducted the work, the group is to identify the individuals who accept direct responsibility for the manuscript. These individuals must fully meet the criteria for authorship defined above. Acquisition of funding, collection of data, or general supervision of the research group, alone, does not justify authorship. All persons designated as authors must qualify for authorship, and all those who qualify are to be listed. Each author must have participated sufficiently in the work to take public responsibility for appropriate portions of the content. All publications (eg, manuscripts, abstracts, oral/slide presentations, book chapters) based on this study must be submitted to Amgen for review. The Clinical Trial Agreement among the institution, investigator, and Amgen will detail the procedures for, and timing of, Amgen's review of publications.

Results Reporting

Results will be reported to clinical study registries in accordance with applicable regulatory requirements. The final summary results will be reported after the global end of study (as defined in Section 4.4) to ensure data from all sites globally are included in the reported results.

Investigator Signatory Obligations

Each clinical study report is to be signed by the investigator or, in the case of multicenter studies, the coordinating investigator.

The coordinating investigator, identified by Amgen, will be any or all of the following:

- A recognized expert in the therapeutic area
- An Investigator who provided significant contributions to either the design or interpretation of the study
- An Investigator contributing a high number of eligible subjects

Data Quality Assurance

All subject data relating to the study will be recorded on printed or electronic CRF unless transmitted to the sponsor or designee electronically (eg, laboratory data, centrally or adjudicated data). The investigator is responsible for verifying that data entries are accurate and correct by physically or electronically signing the CRF.

The investigator must maintain accurate documentation (source data) that supports the information entered in the CRF.

The investigator must permit study-related monitoring, audits, **external review body** review, and regulatory agency inspections and provide direct access to source data documents.

The sponsor or designee is responsible for the data management of this study including quality checking of the data.

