7.3 Final Analysis

The final analysis will be performed after the last subject has had an opportunity to complete the corresponding end of treatment (EOT) visit/procedures.

For the final analysis, data will be subject to ongoing checks for integrity, completeness and accuracy with the expectation that all outstanding data issues are resolved ahead of the final lock.

8. Data Screening and Acceptance

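### The final analysis is keyed to the last subject's end-of-treatment visit in three places and to end of study in protocol 9.4, and nothing reconciles them

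*Protocol*

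**What the plan says.** Three places key the final analysis to the end-of-treatment (EOT) visit:

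- Protocol 9.4.1.3: "The final analysis will be performed after the last subject has had an opportunity to complete the corresponding end of treatment (EOT) visit/procedures".
- The protocol synopsis (1.1) carries essentially the same sentence.
- SAP 7.3 opens with "The final analysis will be performed after the last subject has had an opportunity to complete" the EOT visit, and adds that data will be checked "with the expectation that all outstanding data issues are resolved ahead of the final lock". It gives no other date or cut-off for this analysis.

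Protocol 9.4, the parent section of 9.4.1.3, says otherwise: "the final analysis will be conducted and reported following the end of study, as defined in Section 4.4.1". It gives study integrity as the reason. Section 4.4.1 defines end of study as the last subject's last visit, "following any additional parts in the study (eg, long-term follow-up" (the list then runs into redacted text). Appendix 3, under Results Reporting, also ties the final summary results to the global end of study.

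SAP 5.1 repeats the end-of-study definition, but SAP 7.3 does not refer to it. SAP 10, which lists departures from the protocol's analyses, does not mention the timing of the final analysis.

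**The concern.** One named analysis has two timing statements, and they can lie years apart. The conflict sits inside the current protocol, between 9.4 and its own subsection. It is therefore not a result of the SAP having been written to Amendment 6 while the protocol is at Amendment 7.

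Someone working from the SAP alone would find the EOT milestone, a final lock, and no end-of-study condition. A lock at that milestone would come before two planned streams of data are complete:

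- **Safety.** Treatment-emergent adverse events are a primary endpoint. The safety follow-up visit exists to pick up delayed events, and it falls after EOT.
- **Survival.** Overall survival (OS) is a secondary endpoint followed for up to three years. SAP 5.3 censors at the cut-off any subject known to be alive beyond it.

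No analysis after the final one is planned, so nothing in the plan would bring the remaining data in.

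**Working it through.** The plan states no figure for this gap, so there is none to reproduce. The check is calendar arithmetic on the documents' own windows.

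**Inputs (days after last dose unless stated)**

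- EOT visit: day 0 to 14 (protocol 1.2).
- Safety follow-up (SFU) visit: about day 60 to 65 (protocol 1.1, 8.1.3).
- Adverse-event collection: the later of the SFU visit and 60 days after the end of the dosing interval (protocol 8.2.4.1.1). Assuming a 14-day interval from every-2-week dosing, this is 14 + 60 = day 74.
- Treatment-emergent window for analysis: to day 47 (SAP 5.2).
- Survival follow-up: up to 3 years from first dose (protocol 8.1.4), but from last dose in SAP 5.1.

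**Safety gap for the last subject** = end of window minus EOT day

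| Window | EOT on day 14 | EOT on day 0 |
|---|---|---|
| SFU visit, day 60 to 65 | 60 − 14 = 46; 65 − 14 = 51 | 60 − 0 = 60; 65 − 0 = 65 |
| Adverse-event collection, day 74 (assumed interval) | 74 − 14 = 60 | 74 − 0 = 74 |
| SAP treatment-emergent window, day 47 | 47 − 14 = 33 | 47 − 0 = 47 |

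So the SFU visit falls 46 to 65 days after EOT. Even the shortest of these windows, the SAP's 47 days, is still open at EOT. The same holds for any other subject whose last dose was recent enough to leave the window open. The documents do not let one count them.

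**Survival follow-up still to come at EOT, protocol clock** = 36 − (m + 14/30.44) months, where m is months on treatment and 14/30.44 = 0.46. The documents do not give m, so a range is assumed:

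| m (months) | Remaining follow-up (months) |
|---|---|
| 2 | 33.5 |
| 6 | 29.5 |
| 12 | 23.5 |
| 24 | 11.5 |
| 35.5 | 0.0 |

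On the SAP's last-dose clock it is (m + 36) − (m + 0.46) = 35.5 months whatever the value of m. These figures describe the subject whose EOT sets the milestone. Subjects who started earlier have more follow-up by then.

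**Radiographic progression-free survival (rPFS) and duration of response (DOR).** Treatment runs to progression (protocol 1.1, 1.2). After treatment, protocol 8.1.4 and Table 1-3 footnote e ask for 3-monthly imaging only in subjects who stopped for a reason other than confirmed progression. Only those subjects have later rPFS or DOR information to lose.

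**The case against.** The best answer is that *after* does not mean *at*. The EOT sentences set an earliest time, and an analysis run after end of study satisfies them and protocol 9.4 together. No text names the EOT milestone as the data cut-off, and Appendix 3 points to end of study. Collection is also unaffected: adverse events, serious adverse events and survival are gathered whichever trigger is used. No hypothesis is tested (protocol 9.1), so no error rate is at stake.

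All of that stands, and it makes the data loss conditional on how the trigger is applied. It does not remove the point. A section whose purpose is to fix the timing leaves the cut-off open, by up to years, and the SAP carries no end-of-study condition to close it.

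A reader might infer more than the documents support:

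- *That the plan requires a lock at EOT and will lose these data.* It permits such a lock; protocol 9.4 points the other way.
- *That a fixed share of safety follow-up is lost across the trial.* The gap depends on the day of the EOT visit and on which window is used, and it concerns only subjects still inside that window.
- *That rPFS and DOR would be heavily censored.* Treatment generally continues to progression, and the size of the subgroup that stops without it is not given.
- *That the final analysis could come before the 6-month primary analysis.* This would need every subject, including the earliest enrolled, to be off treatment before the primary analysis falls due. Nothing in the documents supports that.

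**Conclusion.** The concern holds in a limited form. The inconsistency is certain: protocol 9.4, 4.4.1 and Appendix 3 point to end of study, while the synopsis, protocol 9.4.1.3 and SAP 7.3 point to EOT. The consequence is conditional. If the final lock were taken at the EOT milestone, three things would follow:

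- It would come 46 to 65 days before the last subject's SFU visit, and before the adverse-event windows close for any subject still inside them.
- OS would be censored for every subject still alive and in the planned 3-year follow-up. The amount ranges from nearly the whole period to none, depending on treatment duration, which had to be assumed.
- rPFS and DOR would be affected only in subjects who stopped treatment without confirmed progression.

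The effect is on the completeness of a descriptive final data set for a primary safety endpoint and for OS. It is worth correcting because the correction is simple and the protocol has already committed to it.

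**What to change.** In the synopsis, protocol 9.4.1.3 and SAP 7.3, replace the EOT milestone with a statement that the final analysis is performed after end of study as defined in protocol Section 4.4.1. If an EOT-based cut is wanted, give it its own name as an additional analysis.

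The same edit should align the start of the long-term follow-up clock (first dose in the protocol, last dose in the SAP), because end of study depends on it.

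The change is to wording only and needs no new data or procedures. The cost is that the final analysis comes later than an EOT-based lock would allow, which protocol 9.4 already implies.
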